- C. Post Infusion Period 2 Pain & Anxiety Evaluation for 6 days: Participants will complete questionnaires over six days at the investigator's discretion: BPI, NRS, McGill on days 1, 3, and 5 after infusion and HAD and STAI-state and trait questionnaires on day 6 after infusion. Participants will be instructed to mail back the device after completing three days of their last infusion using a prepaid FedEx air bill that will be sent to them by study staff. *Note: The dose oxytocin administration is based on the American College of Obstetricians and Gynecologists' (ACOG) Practice Bulletins for postpartum hemorrhage (see addendum). From the bulletin: Many organizations have recommended active management of the third stage of labor as a method to reduce the incidence of postpartum hemorrhage. Prophylactic oxytocin, by dilute intravenous infusion (bolus dose of 10 units), or intramuscular injection (10 units), remains the most effective medication with the fewest adverse effects". This clinical protocol allows the administration of bolus of oxytocin in a rate of 333 mU/min. We will administer only 1 unit of oxytocin over 40 minutes rate of 25mU/min to avoid any adverse effects.

Texas Children's Hospital REDCap platform may be used for data collection purposes.

Section G: Sample Size/Data Analysis

G1. Sample Size

How many subjects (or specimens, or charts) will be used in this study?

Local: 20 Worldwide: 20

Please indicate why you chose the sample size proposed:

There are no published and validated data regarding the distribution of pain scores in individuals with EDS. From our clinical experience and the fact that the inclusion criteria require patients have chronic pain, it would be reasonable to estimate the mean pain levels without any oxytocin treatment to be 7 on the BPI scale. With a sample size of 17 individuals who will undergo treatment with placebo and oxytocin (i.e., matched pairs), we will be able to detect a mean difference in BPI scores of 2 or greater with oxytocin as compared to the placebo with a two sided test with alpha error of 0.05 and power of 0.8. This analysis is based on an estimated effect size index dz of 0.73, an SD in the oxytocin group of 0.66 x mean, the SD in the placebo group being 1.25 x mean, and the correlation between the measures being 0.15. Additionally, we will enroll 3 more participants to account for a drop out rate of 15%. Thus the total sample size would be 20

G2. Data Analysis

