Provide a description of your plan for data analysis. State the types of comparisons you plan (e.g. comparison of means, comparison of proportions, regressions, analysis of variance). Which is the PRIMARY comparison/analysis? How will the analyses proposed relate to the primary purposes of your study?

The primary goal of this study is to compare the change in pain scores between the pre and post placebo treatment period vs pre and post IV oxytocin treatment period.

Changes from baseline to endpoint will be evaluated by paired T test

Baseline and endpoint that will be compared:

- 1) Maximum pain level, minimum pain level, average pain, and pain-effect scores (using the BPI) in the days prior to each infusion period (placebo and oxytocin) and maximum pain level, minimum pain level, average pain and pain-effect scores (using the BPI) in the days prior to each infusion period (placebo and oxytocin) and average pain and pain-effect scores in the days after each infusion period.
- 2) Comparing the difference in maximum pain level, minimum pain level, average pain and pain-effect scores (using the BPI) pre and post infusion between placebo and oxytocin treatment.
- 3) Simple pain scale scores (NPRS) prior to infusion and simple pain scale scores 2 hours after the infusion on every day of infusion in both infusion periods (placebo and oxytocin).
- 4) Anxiety and depression scores prior and post infusion periods and comparing scores following placebo and oxytocin treatments
- 5) Changes in heart rate, inter-beat-interval (IBI), and physical activity as measured by ACTIHEART comparing data collected prior, during and after placebo and oxytocin treatments.

In addition we will compare heart rate, blood pressure with oxytocin infusion compared to levels with placebo. We will compare oxytocin levels in the plasma prior to the first infusion, immediately after the first infusion and 2 hours after the first infusion for both placebo and oxytocin.

P-values of 0.05 or less will be considered statistically significant

Section H: Potential Risks/Discomforts

H1. Potential Risks/Discomforts

Describe and assess any potential risks/discomforts; (physical, psychological, social, legal, or other) and assess the likelihood and seriousness of such risks:

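### Is the effect size of 0.73 in the sample size section contradicted by the SDs written beside it?

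*Combined protocol and SAP*

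**What the plan says.** Section G1 (Sample Size) first admits the lack of data: "There are no published and validated data regarding the distribution of pain scores in individuals with EDS". It then draws on clinical experience: "it would be reasonable to estimate the mean pain levels without any oxytocin treatment to be 7 on the BPI scale". For 17 matched pairs, a two-sided alpha of 0.05 and power of 0.8, it states that "we will be able to detect a mean difference in BPI scores of 2 or greater with oxytocin as compared to the placebo".

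The inputs follow in one sentence, which opens: "This analysis is based on an estimated effect size index dz of 0.73". The SDs are then given as "an SD in the oxytocin group of 0.66 x mean, the SD in the placebo group being 1.25 x mean". The two measures are taken to correlate at 0.15. Three more participants are added for 15% dropout, giving 20.

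Section G2 (Data Analysis) makes the main comparison one of changes, by paired t test: "The primary goal of this study is to compare the change in pain scores between the pre and post placebo treatment period" against the same change around oxytocin. Its second item lists four BPI quantities for this comparison: "Comparing the difference in maximum pain level, minimum pain level, average pain and pain-effect scores (using the BPI) pre and post infusion between placebo" on the one hand and the active infusion on the other.

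**The concern.** Both SDs are multiples of an unnamed mean. A reader who looks for one in G1 first meets 7. With 7, the two SDs and the correlation of 0.15 give a dz less than a third of the stated 0.73. If that were the intended calculation, the trial would need more than 150 pairs, and 17 would be badly underpowered.

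Even without that reading, dz of 0.73 carries the whole power claim, and it cannot be traced step by step to the figures beside it. G1 does not print the SD of the paired difference. It also does not say whether the SDs and correlation describe scores or changes, or which of the four BPI quantities in G2 they describe.

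**Working it through.** **Inputs from G1:** dz 0.73; difference 2; correlation 0.15; SD multipliers 0.66 (oxytocin) and 1.25 (placebo); mean pain level 7; 17 pairs; two-sided alpha 0.05; power 0.8; dropout 15%. The test, a paired t test, is from G2.

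**Step 1: reproduce the plan's figure.** Exact power of the paired t test (noncentral t, n − 1 degrees of freedom, noncentrality dz × √n):

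- 16 pairs at dz 0.73: 77.9%.
- 17 pairs at dz 0.73: 80.7%, so 17 is the smallest number that reaches 80%.
- Dropout: 17 / (1 − 0.15) = 20.

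The stated size reproduces exactly from dz 0.73. The implied SD of the paired difference is 2 / 0.73 = 2.74 points.

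**Step 2: apply the multipliers to each candidate mean.**

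SD of difference = √(SDo² + SDp² − 2 × 0.15 × SDo × SDp), with SDo = 0.66 × oxytocin mean and SDp = 1.25 × placebo mean; dz = 2 / SD of difference.

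| Mean used (placebo / oxytocin) | SDp | SDo | SD of difference | dz | Pairs for 80% | Power, 17 pairs |
|---|---|---|---|---|---|---|
| Pain level 7 / 7 | 8.75 | 4.62 | 9.26 | 0.216 | 171 | 13% |
| Pain level 7 / 5 | 8.75 | 3.30 | 8.88 | 0.225 | 157 | 14% |
| Mean difference 2 / 2 | 2.50 | 1.32 | 2.65 | 0.756 | 16 | 83% |
| Mean change 1.5 / 3.5 (assumed) | 1.88 | 2.31 | 2.75 | 0.728 | 17 | 80% |
| Mean change 1 / 3 (assumed) | 1.25 | 1.98 | 2.18 | 0.919 | 12 | 94% |
| Mean change 2 / 4 (assumed) | 2.50 | 2.64 | 3.35 | 0.597 | 25 | 64% |

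Example, second row: √(3.30² + 8.75² − 0.30 × 3.30 × 8.75) = √(10.89 + 76.56 − 8.66) = √78.79 = 8.88, and 2 / 8.88 = 0.225.

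Example, fourth row: √(2.31² + 1.875² − 0.30 × 2.31 × 1.875) = √(5.34 + 3.52 − 1.30) = √7.55 = 2.75, and 2 / 2.748 = 0.728.

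**Step 3: test whether 7 can be the multiplied mean.** Assume the BPI score runs from 0 to 10 (the documents do not state its range). The largest possible SD at mean 7 is √(7 × 3) = 4.58. A placebo SD of 1.25 × 7 = 8.75 is then impossible. An SD larger than its mean is unremarkable for a small average change, where individual values fall on both sides of zero. That fits the quantity G2 compares.

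**Step 4: sensitivity to the planning SD.** Power of 17 pairs for a 2-point difference, over an assumed range of the SD of the paired difference: 2.5 gives 87%, 2.74 gives 81%, 3.0 gives 73%, 3.5 gives 60%.

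**The case for a change.** The strongest case for a change is that the written inputs do not determine the sample size. Change pairs that all differ by 2 points call for 12, 17 or 25 pairs under the same multipliers and correlation, and the pair that recovers 0.73 appears nowhere in the documents. Power is sensitive to the SD of the paired difference, which G1 leaves the reader to work out. A clarification would take a few sentences, and it would help anyone interpreting a null result or sizing a later trial.

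The lack of traceability stands. The argument for acting on it is weaker:

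- The SD of the paired difference is one division away, since G1 prints both the difference and dz.
- G1 does not disguise the status of these values. It says no validated data exist, appeals to clinical experience and calls dz estimated.
- The planning SD does not enter the analysis. The paired t test uses the observed SD, and a null result or a follow-on trial would be judged on the observed estimate and its variability.
- Rewriting the sentence to say that the SDs refer to changes would presume something the documents do not establish.

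Which of the four BPI quantities was powered is a question of endpoint definition. It does not bear on whether dz of 0.73 is wrong.

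**Conclusion.** A contradiction is not shown. An input whose reference mean is undefined cannot contradict dz of 0.73, and the reading that produces the large gap (dz about 0.22 to 0.23) requires an SD that a 0 to 10 scale cannot produce. Two other readings land on or near the plan: the printed mean difference of 2 gives dz 0.756 and 16 pairs, and assumed mean changes of 1.5 and 3.5 give 0.728 and 17 pairs. The documents do not settle which was used.

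The figures that fix the trial's size are consistent with one another: dz 0.73, 17 pairs, 80.7% power, 20 enrolled. What is left is incomplete description of planning guesses in a study labelled a pilot. Filling it in would correct no figure shown to be wrong, and would change neither the enrolment, the paired t test nor the power claim. That claim remains conditional on an SD of the paired difference of about 2.74 points, as any such claim would be. The conclusion rests on the assumed 0 to 10 range only for ruling out 7; that the reference mean is undefined does not depend on it.

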Hypermobile EDS is more prevalent in females and the symptoms are usually more severe in females and more females come to medical attention. Oxytocin secretion in the body is dynamic and can be affected by multiple factors including the menstrual period. In order to have minimum variation between tested individuals we chose to conduct this study in females, all participants will be at the same stage of their menstrual cycles. We are not aware of any difference in the risk from using oxytocin in females vs males.

All participating individuals will be individuals affected with hypermobile-EDS (hEDS) with chronic moderate pain. Study will include two periods of treatment - one with placebo and one with oxytocin. Each period of treatment will include three consecutive daily infusions (placebo or oxytocin). Each participant will receive placebo infusion (normal saline) in the first treatment period and oxytocin infusion in the second treatment period. Each period will be preceded by 6 days of daily pain evaluation using pain-evaluation questionnaire ('pre-infusion evaluation'). This period (prior to placebo or prior to oxytocin treatment) will start 1-3 days after the end of the menstrual cycle. Participants will be blinded to the order of treatment.

For each treatment period, participants will arrive to the study site for three daily consecutive visits, each will last for 3-4 hours. Response variables will be collected prior, during and after each infusion. Patients will fill out pain evaluation questionnaires pre and post infusion. Blood pressure and heart rate measurements will be taken prior, during and after the infusion. Blood samples for measurements of oxytocin levels and blood samples for future analysis will be collected prior and after the infusion. Response to treatment by questionnaire will be evaluated also during 6 days after each three infusion days (placebo or oxytocin). Patients will be asked to wear the ACTIHEART device 3 days prior to infusion, during the 3 days of infusions, and in the 3 days after the last infusion.

Inclusion Criteria:

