1) Premenopausal Females, Age >18 years 2) Clinical diagnosis of hypermobile EDS according to the 2017 criteria for hEDS 3) Menstrual periods (range from 8 to 42 days) 4) Pain level greater that pain score of 4 out of 10 on a Numeric Rating Scale in at least two of the following locations: back, neck, shoulders, elbows, wrist, hand joints, hips, knees, ankles, on most days over the 3 months preceding enrollment. 5) On a stable regimen for pain control without any expected increase in dose of pain medications during the study period. 6) All participants should have a negative urine pregnancy test and agree to use an acceptable method of contraception (abstinence or barrier methods). 7) Current from the last year EKG report prior to the infusion for screening purposes. Otherwise, participant will need to have an EKG done in person at the screening visit on site.

Exclusion Criteria:

1) Known allergy to OXT or preservatives in the medication 2) Pregnancy 3) Lactation 4) A confirmed clinical diagnosis of autoimmune disorders that lead to joint inflammation and joint pain such as SLE, RA, psoriatic arthritis, ankylosing spondylitis, scleroderma, and enteropathic arthritis 5) History of known cardiac arrhythmias (except for asymptomatic sinus tachycardia and sinus bradycardia) 6) Heart rate persistently greater than 110/min or less than 50 per minute 7) QTC of > 450 ms from EKG (electrocardiogram) test 8) Taking oral or other hormonal contraceptives 9) Individuals with a clinical condition which, in the view of the investigator compromises safety 10) Participating in another interventional study.

F2. Procedure

This will be a single-blind, fixed-sequence study. This study will include two treatment periods. During the first period, placebo will be administered and during the second period, oxytocin will be administered. The participants will be blinded to the sequence of treatment assignment.

Each treatment period will start 7-12 days after the first day of menstruation and will be divided to the following: 1) preinfusion period of 6 days during which baseline pain and anxiety evaluation will be done, 2) infusion period that includes 3 consecutive days of infusions, 3) post-infusion evaluation period of 6 days during which post-treatment pain and anxiety will be evaluated.

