- A. Pre-infusion Period 1 (will last six days prior to infusion): 1) Questionnaires: Subjects will be asked to complete painevaluation questionnaires (BPI, NRS, and McGill). Anxiety evaluation will be completed by patients using HAD and STAltrait and state parts questionnaires. 2) Participants will be asked to wear the ACTIHEART device during 3 days prior to the infusion, during the 3 infusion days, and in the three days after the infusion. The instructions for the Actiheart monitor and activity record including patient visit reminders will be provided to subjects.
- B. Infusion period 1 (Placebo Infusion over three days): Participants will arrive for three consecutive day visits. 1) Subject will be instructed to eat a light, non-fatty breakfast. 2) Vital signs (blood pressure and heart rate), including weight and height will be collected prior to infusion. 3) Provide two questionnaires (BPI, NRS) for subjects to complete. 4) Nursing staff will establish IV access for infusion and blood collection. 5) Prior to infusion, blood samples will be obtained for oxytocin levels and for storage. 6) Placebo infusion (200ml, 0.9% NaCl, over 40 minutes). Blood pressure and heart rate will be monitored during and after the infusion. 7) Blood sample (for oxytocin levels and storage) will be collected immediately after the infusion on day 1. Note: This will require a second vein access to be set prior to the infusion (this sample can not be collected from the place of the OXT / Placebo infusion). 8) Administer both the NPI and STAI-state part questionnaires prior to subject's discharge. Subjects will be discharged 2 hours after the infusion.
- C. Post Infusion Period 1 Pain & Anxiety Evaluation for 6 days: Participants will complete questionnaires over six days at the investigator's discretion: BPI, NRS, McGill on days 1, 3, and 5 after infusion and HAD and STAI-state and trait questionnaires on day 6 after infusion.

Treatment period 2 will start at least 2 weeks after the completion of treatment period 1 and 7-12 days after the first day of menstruation for subjects. Treatment period 2 will consist of the following:

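### With placebo always first and a paired t test, a woman who leaves after period 1 drops out of the primary contrast, which is biased if leaving is related to her placebo response

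*Combined protocol and SAP*

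**What the plan says.** Section F2 describes the design: "This will be a single-blind, fixed-sequence study". F1 gives the order: "Each participant will receive placebo infusion (normal saline) in the first treatment period and oxytocin infusion in the second treatment period". Participants are not told the sequence. F2 separates the periods: "Treatment period 2 will start at least 2 weeks after the completion of treatment period 1", with the start also tied to the menstrual cycle.

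G2 states the primary goal as to "compare the change in pain scores between the pre and post placebo treatment period vs pre and post IV oxytocin treatment period", and the method as "Changes from baseline to endpoint will be evaluated by paired T test". Item 2 of its list is the between-treatment contrast: the difference in BPI scores "pre and post infusion between placebo and oxytocin treatment". Item 1 covers pre-post comparisons within each period.

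G1 counts complete pairs, "With a sample size of 17 individuals who will undergo treatment with placebo and oxytocin (i.e., matched pairs", and then adds a margin: "Additionally, we will enroll 3 more participants to account for a drop out rate of 15" percent. Dropout is treated there only as a loss of numbers. The documents give no analysis set, missing-data method or sensitivity analysis for the pain scores. The withdrawal text in Section N concerns blood and urine samples.

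**The concern.** In a crossover with randomised order, women who leave after the first period come from both treatments. Here each of them has a placebo change and no oxytocin change. A paired test of item 2 needs both, so the analysed set is selected after one of the two outcomes has been observed.

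That is harmless if women leave for unrelated reasons. It is not harmless if the placebo result influences who comes back. A woman who felt no benefit may see no point in three more site days; one who feels better may not want them either. If poor placebo responders leave, the completers' placebo mean looks too good and the oxytocin effect is understated. If good placebo responders leave, the effect is overstated. The placebo changes needed to adjust for this will already have been collected.

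**Working it through.** **G1's figure.** For a paired t test with dz = 0.73, 17 pairs and two-sided alpha 0.05, exact power from the noncentral t distribution is 0.807, and 17 is the smallest number of pairs that reaches 0.80. Allowing for 15% loss, 17/0.85 = 20. G1's sample size reproduces. The implied SD of the paired difference is 2/0.73 = 2.74, so the standard error with 17 pairs is 2.74/√17 = 0.66.

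**SDs of the changes (assumption).** G1 gives SDs of 0.66 × mean (oxytocin) and 1.25 × mean (placebo) and a correlation of 0.15, without saying which mean. Applied to pain levels of 5 and 7 they give SDs of 3.30 and 8.75 and dz of only 0.23, which does not match G1. I therefore apply them to mean improvements of m on placebo and m + 2 on oxytocin, and require the SD of the difference to be 2.74:

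(0.66(m+2))² + (1.25m)² − 2(0.15)(0.66)(1.25)m(m+2) = 2.74²

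This gives m = 1.49, so the mean improvements are 1.49 and 3.49. The SDs are 1.25 × 1.49 = 1.87 (placebo) and 0.66 × 3.49 = 2.31 (oxytocin).

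**How much selection reaches the estimate.** The slope of the oxytocin-minus-placebo difference on the placebo change is 0.15 × 2.31/1.87 − 1 = −0.81. Most of any selection on the placebo change therefore passes into the contrast, with the sign reversed.

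**Bound.** Suppose exactly the three most extreme of 20 placebo changes are lost. The expected top three of 20 standard normal values are 1.867, 1.408 and 1.131, so the mean of the other 17 shifts by 4.406/17 = 0.259 SD. The bias is 0.259 × 1.87 × 0.81 = 0.39 points.

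**Weaker dependence.** If a woman's tendency to leave correlates c with her placebo change, the bias is about c × 0.39. Simulation (40,000 trials, 20 enrolled, 3 lost after period 1, true difference 2 points) agrees:

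| Correlation of leaving with placebo change | Mean estimate, poor responders leave | Mean estimate, good responders leave | Two-sided type I error (nominal 0.05) |
|---|---|---|---|
| 0 (random) | 2.00 | 2.00 | 0.05 |
| 0.3 | 1.88 | 2.12 | 0.054 |
| 0.5 | 1.80 | 2.20 | 0.06 |
| 0.7 | 1.72 | 2.28 | 0.07 |
| Three extreme responders leave (bound) | 1.61 | 2.40 | 0.10 |

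At the bound with poor responders leaving, power falls from 0.81 to about 0.67. If only one woman is lost at correlation 0.5, the estimate averages 1.93 or 2.08 and the error rate stays near 0.05.

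**Sensitivity to the SDs.** Keeping G1's SD ratio (0.66/1.25 = 0.528) and rescaling to a difference SD of 2.74 gives SDs of 1.37 and 2.59 and a slope of 0.15 × 0.528 − 1 = −0.92. The bound becomes 1.38 or 2.62, with type I error about 0.19 to 0.20. With equal SDs, the bias at the bound falls from 0.46 at correlation 0.15 between the two changes to about 0.28 at 0.7.

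**Alternative analysis.** A maximum likelihood estimate that keeps the leavers' placebo changes averages 2.00 in every row of the table. Under random loss its standard error is 0.653, against 0.665 for the completers' t test.

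**The case against.** The strongest reply is that informative leaving is conjecture. G1's 15% is an overall allowance with no timing or cause, so it also covers loss within either period. Section L pays 200 dollars per completed period and reimburses travel, and cycle-timed scheduling makes logistical loss at least as plausible. Under random loss the paired t test is unbiased. This stands, and it is why the point is conditional.

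It is also fair that the bound needs all three losses to fall between periods and to be exactly the extreme responders. At correlations of 0.3 to 0.5 the bias is 0.12 to 0.20 points, or about 0.2 to 0.3 standard errors (0.12/0.66 and 0.20/0.66). This is a pilot, and at most about three women are affected.

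The mixed model's zero bias in the simulation is partly built in, because leaving there depends only on the observed placebo change and chance. If leaving depends on unrecorded factors related to the later oxytocin response, the model can be biased too.

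What the reply does not answer is that the plan has no rule for these women, and that a method exists which needs a weaker assumption and loses nothing when everyone returns.

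**Conclusion.** The point holds in conditional form. The paired analysis of G2 item 2 cannot use a woman who has only the placebo period, and the fixed order means that every between-period loss is of this kind. If leaving is related to the placebo response, the bias is roughly 0.1 to 0.3 points on a 2-point target at correlations of 0.3 to 0.7, with 0.39 as the bound. These figures rest on three losses, all between periods, and on the stated reading of G1's multipliers.

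A reader might infer three stronger things that the documents do not support:

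- **That the primary result will be biased, or biased in favour of oxytocin.** Nothing shows that such leaving will occur, or in which direction.
- **That false positives rise more than threefold.** At the bound, with good responders leaving, rejection in favour of oxytocin is 9.0% against 2.5%. That counts one tail only; the plan's test is two-sided, and there the figure is about 10% against 5%.
- **That a leaver's placebo data are thrown away.** No such rule is written. The exclusion follows from pairing, and her data remain usable under item 1.

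This should be changed before analysis, but it does not undermine the trial.

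**What to change.** In G2, specify that the primary contrast is estimated from a linear mixed model of each participant's period-specific change, with treatment as fixed effect, an unstructured 2×2 within-participant covariance and Kenward-Roger degrees of freedom. Include every participant with a change in at least one period, and report the completers' paired t test beside it.

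The cost is a sentence or two in G2 and standard software, with no extra data or participants. With no losses the model equals the paired t test, so G1's power statement stands. Under random loss the gain in precision is negligible; the reason for the change is protection against selection on the placebo response. The downside is small. The model assumes that leaving is explained by observed data, which is weaker than the completers' requirement that it be unrelated to the placebo response. It does not separate treatment from period, which the fixed order confounds under either analysis.

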In this study, we seek to investigate the potential effect of IV oxytocin on chronic pain and its functional consequences in individuals with hypermobile Ehlers Danlos syndrome. Chronic pain will be assessed both by pain scales and by patient-reported outcomes. Functional consequence of chronic musculoskeletal pain will be evaluated using ACTIHEART - a chest-worn device using self-adhesive ECG electrodes that records heart rate, inter-beat-interval (IBI), and physical activity.

Section D: Purpose and Objectives

The purpose of this pilot study is to evaluate effect of IV oxytocin on chronic pain in patients with hypermobile Ehlers Danlos syndrome. The study will evaluate chronic pain before and after treatment with IV oxytocin.

Primary outcome measure 1) Change in the individual's subjective reported pain following treatment with placebo

compared to the change in reported pain following treatment with oxytocin as assessed by the following questionnaires: Numerical pain rating scale, Brief Pain Inventory, and McGill Pain Questionnaire.

Secondary Outcome measures 1) Change in heart rate patterns and activity level following treatment with placebo compared to the change in heart rate patterns and activity level following treatment with oxytocin as an objective functional outcome of pain. 2) Change in reported signs of depression and anxiety following treatment with placebo compared to the change in the reported signs following treatment with oxytocin as assessed by Hospital anxiety and depression scale and State-Trait Anxiety Inventory questionnaires.

Section E: Protocol Risks/Subjects

E1. Risk Category

Category 2: Research involving greater than minimal risk, but presenting the prospect of direct benefit to the individual subjects.

E2. Subjects

Gender:

Female

Age:

Adult (18-64 yrs)

Ethnicity:

All Ethnicities

Primary Language:

English

Groups to be recruited will include:

Patients

Which if any of the following vulnerable populations will be recruited as subjects?

Vulnerable populations require special protections. How will you obtain informed consent, protect subject confidentiality, and prevent undue coercion?

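### G2 item 3 does not say how the three daily NRS changes are combined or which day decides; tested day by day, a false significant oxytocin day has a chance of about 9% to 14%

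*Combined protocol and SAP*

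**What the plan says.** The primary outcome in Section D is the change in reported pain under placebo compared with that under oxytocin, measured by three instruments: "Numerical pain rating scale, Brief Pain Inventory, and McGill Pain Questionnaire". G2 describes the main goal as being to "compare the change in pain scores between the pre and post placebo treatment period vs pre and post IV oxytocin treatment period". It then gives one method for all the comparisons it lists: "Changes from baseline to endpoint will be evaluated by paired T test".

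Item 3 in that list sets the pre-infusion score against "simple pain scale scores 2 hours after the infusion on every day of infusion in both infusion periods (placebo and oxytocin"). F1 fixes the number of days: "Each period of treatment will include three consecutive daily infusions (placebo or oxytocin"). The rule for every item is "P-values of 0.05 or less will be considered statistically significant".

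The documents name no deciding infusion day, no average over days, no repeated-measures model and no multiplicity adjustment.

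The sample size in G1 is 17 evaluable pairs, based on the BPI, for a "two sided test with alpha error of 0.05 and power of 0.8".

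In F2, the pre-infusion step of each infusion visit names the BPI and NRS. The discharge step, 2 hours after infusion, names an instrument abbreviated NPI together with the STAI-state. NPI is not defined, and the NRS is not named at that step in either treatment period.

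**The concern.** A paired t test takes one difference per participant. Item 3 supplies three per period and does not say how to reduce them to one. If the three oxytocin days gave, say, p = 0.03, 0.20 and 0.40, the plan would support reporting a significant acute response and would equally support reporting none. The choice would be made after seeing the data.

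Two things are at stake. The error rate for this item is above 5% if any one day can be claimed. And three repeats of the same measurement, used separately, give less power than their mean, which matters with 17 pairs.

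**Working it through.** **Inputs.** From G1: 17 evaluable pairs, 20 enrolled, two-sided alpha 0.05, power 0.80, standardised paired effect dz = 0.73 (for the BPI, oxytocin versus placebo). From F1: three infusion days per period. From G2: paired t test, p ≤ 0.05. Not in the documents: the between-day correlation ρ of the daily NRS changes, and any effect size for the 2-hour NRS change. The correlation of 0.15 in G1 is between the oxytocin and placebo measures, not between days. I therefore let ρ run from 0 to 0.9, equal for all pairs of days.

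**The plan's own figure.** For n = 17 and dz = 0.73 the noncentrality is 0.73 × √17 = 3.01 on 16 degrees of freedom. Power is 0.807, and n = 16 gives 0.779, so 17 is reproduced. Allowing for 15% dropout, 17 / 0.85 = 20, which is also reproduced.

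**False significant day, three daily tests on oxytocin.** With independent days the chance of at least one is 1 − 0.95³ = 0.143. In the relief direction only it is 1 − 0.975³ = 0.073. For correlated days, simulation of three equicorrelated paired t tests (n = 17, no true pre-to-post change, 300,000 trials per setting) gives:

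| ρ between days | any day, either direction | any day, relief direction |
|---|---|---|
| 0 | 0.142 | 0.073 |
| 0.3 | 0.137 | 0.069 |
| 0.5 | 0.126 | 0.062 |
| 0.8 | 0.101 | 0.050 |
| 0.9 | 0.086 | 0.043 |

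The nominal values are 0.05 and 0.025. With n = 20 the results are almost the same (0.143 at ρ = 0 and 0.086 at ρ = 0.9, either direction). Three daily oxytocin-minus-placebo contrasts, each a paired t test on 17 differences, would have the same error rates, with ρ then the between-day correlation of those contrasts.

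**Precision from averaging.** The standard error of the three-day mean relative to one day is √((1 + 2ρ)/3), which is 0.73, 0.82 and 0.93 at ρ = 0.3, 0.5 and 0.8. If the effect is similar on each day, dz is divided by that factor:

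| dz per day | power, one day | three-day mean, ρ = 0.3 | ρ = 0.5 | ρ = 0.8 |
|---|---|---|---|---|
| 0.5 (illustrative) | 0.49 | 0.76 | 0.66 | 0.55 |
| 0.73 (borrowed from the BPI) | 0.81 | 0.97 | 0.93 | 0.86 |

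Every entry is at n = 17 and two-sided 0.05.

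**The case against.** The strongest reply is that the text never says the days are tested separately. The reference to every infusion day may only describe when scores are taken, and averaging is not ruled out. That stands: what the documents establish is silence on how the days are combined. The error rates and the lost precision follow only from the daily-test reading. But silence leaves that reading open, and it is the natural one for a paired t test.

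A reader might infer that item 3 is a primary analysis because the NRS is a primary questionnaire. The documents do not support this. The NRS is also collected in the pre-infusion days and on days 1, 3 and 5 after infusion. The stated goal is change across treatment periods, the sample size rests on the BPI, and nothing designates the 2-hour score as primary.

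A reader might quote a single figure of about 13%. That needs ρ of roughly 0.3 to 0.5, which the documents do not give, and it counts days on which pain worsens as well as days of relief.

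A reader might count all six day-by-period tests. With independent periods this gives 1 − (1 − 0.1264)² = 0.24 at ρ = 0.5 and 1 − (1 − 0.1366)² = 0.25 at ρ = 0.3. But three of those tests are on placebo and cannot produce a false oxytocin claim.

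It is also fair that this is a pilot, and that the gain from averaging is small if days correlate highly. Neither removes the point: G2 still declares significance at 0.05, and one sentence closes the gap.

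**Conclusion.** The point holds in a limited form. Item 3 does not say which day decides or how the three days are combined. Read as daily tests, it carries a chance of about 9% to 14% of at least one falsely significant oxytocin day at n = 17 (ρ from 0.9 to 0), or about 4% to 7% in the relief direction against 2.5%. These figures rest on equal between-day correlation and no true pre-to-post change. Because item 3 states no oxytocin-minus-placebo contrast, a placebo response could make days significant more often still, without any drug effect.

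The power comparison assumes a similar effect each day. The value 0.5 is illustrative, and 0.73 belongs to a different instrument.

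This is a worthwhile clarification of an acute measure that the plan does not label primary. It does not show that the primary analysis is invalid. The wider question of which comparison in G2 is primary remains open whatever is done here.

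**What to change.** Rewrite item 3 along these lines: for each participant and each period, take the 2-hour minus pre-infusion NRS change on each of the three infusion days and average the three; compare the oxytocin and placebo averages in one two-sided paired t test at 0.05. Present the day 1, day 2 and day 3 contrasts descriptively with 95% confidence intervals and no claim of significance. This brings the error for item 3 back to 5% and matches the between-period goal stated in G2. A mixed model across days would be an acceptable alternative if fixed in advance.

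In F2, replace or define NPI in the discharge step of both treatment periods, so that it is clear the NRS is collected 2 hours after infusion.

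The cost is a sentence or two in G2 and one correction in F2. If NPI is a slip for the NRS, no new data are needed; otherwise one short scale is added at discharge. The statistical downside is that an effect confined to one day is diluted in the average, though it remains visible in the daily results. The change controls error for item 3 only: the BPI comparisons and the choice of a single primary comparison still need their own decision.
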